9.3.4. Risk Factors for Malignancy

Risk factors for malignancy will be identified during the 12 months prior to and including index date:

- Age >65 years
- History of malignancy
- History of NMSC
- Obesity
- Alcohol-related conditions
- Tobacco-related conditions

9.3.5. Risk Factors for CVD

Risk factors for CVD will be identified during the 12 months prior to and including index date:

- Age >65 years
- Diabetes
- Obesity
- Hypertension
- Hyperlipidaemia
- Chronic kidney disease
- Alcohol-related conditions
- Tobacco-related conditions

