9.3.3. Risk Factors for Thromboembolic Events

Risk factors for thromboembolic events will be identified during the 12 months prior to and including index date:

- Age >65 years
- History of VTE
- History of arterial thromboembolism (ATE)
- Major surgery within 90 days before the index date
- Combined hormonal contraceptives
- Hormone replacement therapy
- Pregnancy
- Malignancy
- CVD

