	ICD-10-CM codes to ICD-10 equivalents whenever feasible)			

Table 1. Preliminary Definitions of the Main Study Variables

Risk factors for thromboe	mbolic events, malignancy or C	CVD			
Age 65 years or older	per date of birth				
History of thromboembolic events including VTE or ATE	ICD-10 codes I26, I260A I269 I82.2; I82.3, I82.8, I82.9 O22.3 Denmark only: O882D, O882E	3, O87.0, O87.1	, I81, I82.0,		
Malignancy (any, primary or secondary)	ICD-10 codes chapter C	ICD-10 codes chapter C, treatment codes if relevant	ICD-10 codes chapter C		
Major surgery within 90 days of index date	NOMESCO Classification of Operations on the nervous system: KA; Operations on endocrine organs: KB; Operations on the heart and large intrathoracic vessels: KF; Operations on respiratory organs, chest, mediastinum and diaphragm: KG; Breast surgeries: KH; Operations on digestive organs and spleen: KJ; Operations on the urinary tract, male genitalia and retroperitoneal tissue: KK; Operations on female genitalia: KL; Obstetric operations: KM; Operations on the musculoskeletal system: KN	CCAM codes for major surgery	•		
Combined hormonal contraceptives	ATC codes G03A		Not available (not reimbursed)		
Hormone replacement therapy	AT	C codes G03			
Obesity	ICD-10 codes E65				
Alcohol-related conditions	ICD-10 codes K70, F10				
Tobacco-use related conditions	ICD-1	0 codes J40-J47			
Diabetes	ICD-10 codes F	E10-E14, ATC codes A10	1		

Table 1. Preliminary Definitions of the Main Study Variables

Hypertension	ICD-10 codes I10-I15, treatment proxies			
Hyperlipidaemia	ICD-10 codes E78, treatment p	proxies, laboratory data (l	Denmark only)	
Coronary artery disease	ICD-10 codes I21-I25 Nordic Medico-Statistical Committee (NOMESCO) codes for coronary artery bypass graft (CABG) or percutaneous intervention (PCI): FNF, FNG, FNA, FNB, FNC, FND, FNE	ICD-10 codes I21-I25	ICD-10 codes I21-I25 Nordic Medico- Statistical Committee (NOMESCO) codes for coronary artery bypass graft (CABG) or percutaneous intervention (PCI): FNF, FNG, FNA, FNB, FNC, FND, FNE	
Chronic kidney disease	ICD-10 codes N18, potentially dialysis procedure codes	ICD-10 codes N18	ICD-10 codes N18, potentially dialysis procedure codes	
AA diagnosis	ICD	0-10 code L63		

Source of ICD-10 codes: Denmark and Sweden, inpatient (hospital) or outpatient (specialist visits); France, inpatient hospital encounters. ICD-10 codes with trailing letters are applicable in Denmark only.

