9.7. Data Analysis

This is a descriptive study and the data will be analysed and results presented separately by country. Counts and proportions for categorical variables and mean and median with ranges for continuous variables will be calculated to address the study objectives, as below. All proportions will be reported with 95% CIs.

Data sources vary in collection of laboratory test and vaccine information (data on both laboratory tests and their results are available in Denmark; data on performed laboratory tests, but not results, are available in France; laboratory data are not available in Sweden). Data on vaccines are not available in Sweden.

Counts and proportions will be calculated for:

- 1. Patients with evidence of having performed the following laboratory tests and screenings within 3 months before index date:
 - Lymphocyte count
 - Platelet count
 - Screening for TB
 - Screening for viral hepatitis B and C
- 2. Patients with evidence of having performed the following laboratory tests at week 4 (\pm 2 weeks) after index date:
 - Lymphocyte count
 - Platelet count

- 3. Patients with evidence of having received live attenuated vaccines within 4 weeks before index date
- 4. Patients with evidence of having received live attenuated vaccines during treatment with ritlecitinib
- 5. Females in whom pregnancy, as recorded in the available data sources, overlaps with ritlecitinib use
- 6. Patients aged <12 years on the index date
- 7. Patients with a serious infection before index date
- 8. Patients with evidence of having measured risk factors and the number of measured risk factors for thromboembolic events within 12 months before index date
- 9. Patients with evidence of having measured risk factors and the number of risk factors for malignancy within 12 months before index date
- 10. Patients with evidence of having measured risk factors and the number of risk factors for CVD within 6 months before index date

The windows for ascertainment of presence of specific events may be revised to reflect the local data flow.

Detailed methodology for summary and statistical analyses of data collected in this study will be documented in a SAP, which will be dated, filed, and maintained by the sponsor. The SAP may modify the plans outlined in the protocol; any major modifications of primary endpoint definitions or their analyses would be reflected in a protocol amendment.

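### Section 9.3.5 leaves established cardiovascular disease off the CVD risk-factor list, so item 10 of Section 9.7 does not count it, although item 8 does

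*Protocol*

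**What the plan says.** The protocol sets up three risk-factor lists for objective 2.

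- Section 9.3.3 (thromboembolic events) includes "History of VTE", a history of arterial thromboembolism, and CVD as a separate item.
- Section 9.3.4 (malignancy) includes "History of malignancy" and a history of non-melanoma skin cancer.
- Section 9.3.5 (CVD) opens with "Risk factors for CVD will be identified during the 12 months prior to and including index date". Its eight items are age over 65, diabetes, obesity, hypertension, hyperlipidaemia, chronic kidney disease, alcohol-related conditions and tobacco-related conditions.

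Table 1 in Section 9.3.7 has a row "Coronary artery disease" (ICD-10 I21-I25, with bypass and percutaneous intervention codes in Denmark and Sweden). It stands under one heading covering thromboembolic events, malignancy and CVD, between hyperlipidaemia and chronic kidney disease.

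Item 10 of Section 9.7 plans counts and proportions for "Patients with evidence of having measured risk factors and the number of risk factors for CVD within 6 months before index date". Item 8 does the same for thromboembolic risk factors. Section 9.9 says that these results describe the exposed population and cannot show whether the prescriber weighed the risks.

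**The concern.** Two of the three lists treat an earlier occurrence of the outcome as a risk factor for that outcome. The CVD list does not, and the protocol gives no reason for the difference. Nothing restricts 9.3.5 to first-ever CVD. Table 1 adds to the doubt, because it defines a coronary variable and places it between two items of the CVD list, while the list itself does not name it.

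At stake is the reading of item 10. Objective 2 asks for a description of users' CVD risk factors before treatment starts, and Section 9.9 discusses that description with reference to patients at high risk. A reader who takes item 10 as the study's statement on cardiovascular risk would not see prior coronary disease or stroke in it. Some users with such a history could be shown as having no CVD risk factor.

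**Working it through.** The protocol gives no figure to reproduce, so the check compares the lists and then applies them to example users.

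| List | Counts history of its own outcome? | Counts CVD? | Reported in 9.7 |
|---|---|---|---|
| 9.3.3 thromboembolic | Yes, venous and arterial | Yes, as its own item | Item 8 |
| 9.3.4 malignancy | Yes, including skin cancer | No | Item 9 |
| 9.3.5 CVD | No | No | Item 10 |

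Each example user is aged 65 or younger by the 9.3.5 cut-off (under 65 if the age row of Table 1 is used). The event is coded within the last 6 months, so the result is the same under the 12-month window of 9.3.5 and the 6-month window of item 10.

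1. *Infarction code (I21) and none of the eight listed factors or their treatment proxies.* Item 10 scores 0. Item 8 scores at least 1, through CVD.
2. *The same user with treated hypertension.* Item 10 scores 1 and would score 2 if history of CVD were a list item. The user is flagged, but with one factor fewer.
3. *Stroke code only.* Item 10 scores 0. Whether item 8 counts the user depends on how arterial thromboembolism and CVD are coded. In the text of Table 1 available here, the thromboembolism row shows only venous and pulmonary codes (such as I26, I81, I82), and there is no stroke row and no row for CVD as such.
4. *If the coronary row of Table 1 is read into 9.3.5.* User 1 moves from 0 to 1 and user 2 from 1 to 2. User 3 stays at 0.

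The size can be written in general form. Let p be the share of users with established CVD, and q the share of those users who have none of the eight listed factors. If history of CVD were added as one item:

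- the mean number of CVD risk factors per user would rise by p × 1 = p;
- the proportion with at least one factor would rise by p × q.

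The documents give neither p nor q, so neither shift can be computed. Because q cannot exceed 1, the shift in the proportion is at most p. It is smaller to the extent that these users are already flagged through age, diabetes, or the treatment proxies for hypertension and hyperlipidaemia.

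**The case against.** The strongest reply is that nothing is lost. CVD and arterial thromboembolism are items in 9.3.3, item 8 reports them, and Table 1 already defines coronary disease. This stands for the study as a whole. A reader might infer that the protocol fails to describe users with prior infarction at all, or that it understates cardiovascular risk throughout. The documents do not support that, because the gap lies only in item 10. It does not remove the gap, since a count of thromboembolic risk factors does not tell the reader of item 10 how many users have established CVD.

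A second reply is that risk factors for CVD may properly mean antecedents, kept apart from the disease itself. That is a legitimate design, and no section requires the three lists to be built alike. The protocol does not say that this is the intent, however, and its other two lists follow the opposite rule.

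Third, Section 9.3.7 calls the definitions preliminary and leaves refinement to the SAP, and Section 9.7 lets the SAP modify the plans. The SAP may therefore place the coronary row in the CVD list. But 9.3.5 is an enumerated list, and which items belong to it is a different matter from how each is coded. Taking in the coronary row alone would also still leave out stroke.

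Finally, many users with an infarction or stroke would carry another listed factor or a treatment proxy. That is plausible and limits the error in the proportion with at least one factor. It does not correct the number of factors.

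**Conclusion.** The omission is real and its effect is narrow. As written, item 10 excludes prior CVD from the count. It can report a user aged 65 or younger with a recent infarction code as free of CVD risk factors, while item 8 counts the same user. The objective 1 adherence indicators are not affected, and objective 2 is descriptive.

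The conclusion assumes that 9.3.5 is applied as listed and that CVD in 9.3.3 covers coronary disease. The stroke part depends on the text of Table 1 available here, which may be incomplete.

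The size is unknown. A reader might attach a number to it: an assumed prevalence of 0.5% to 3% applied to 385 users gives 385 × 0.005 = 1.9 to 385 × 0.03 = 11.6 patients per database. The documents do not support this as an estimate. They give no prevalence, and 385 is the precision target of Section 9.5 rather than expected enrolment. A reader might also infer that most users with prior CVD would land in the no-risk-factor group. The text shows only that some can.

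**What to change.** - Add history of CVD to Section 9.3.5 and to item 10, using the coronary artery disease row that Table 1 already contains.
- Add arterial and stroke codes to Table 1, so that arterial thromboembolism and stroke can be counted in both 9.3.3 and 9.3.5. The variables now defined there do not supply stroke.
- Report established CVD as its own row, so that item 10 can be read with and without it. Under Section 9.10, a count of 1 to 4 in that row would be masked.

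If the sponsor does intend a list for first-ever CVD, one sentence in 9.3.5 saying so, together with the separate row, would meet the point.

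The cost is a short extra code list and one more table row. The reported CVD risk burden would be slightly higher. Section 6 plans the start of data extraction for September 2027, so the change can be made before any data are drawn.

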9.3.6. Other Variables

Demographics

- Age at index date
- Sex
- Calendar year of index date

9.3.7. Preliminary Operational Definitions of the Main Study Variables

Generally, in the participating data sources, disease is identified by diagnoses recorded at hospitalizations (all three countries) or at hospital-based specialist outpatient clinics (Denmark and Sweden). Diagnoses are currently coded using the World Health Organization (WHO) International Classification of Diseases, Tenth Revision (ICD-10). The Danish version of the ICD-10 may have more detailed codes compared with the WHO ICD-10. ICD-11 will be used if introduced during the study period. Treatment records originate, depending on the database, from outpatient dispensings, from hospital administrations, and are coded using the Anatomical Therapeutic Chemical (ATC) classification or local structured vocabularies (e.g., local treatment codes in Denmark). Ritlecitinib and concomitant medications and vaccinations will be identified using ATC codes or hospital treatment codes as appropriate. Data on laboratory tests, available from Denmark and France, will be identified using Nomenclature, Properties and Units (NPU) codes or local codes as appropriate. Surgeries will be defined using country-specific procedure/surgery codes. Age (date of birth) and sex will be used as reported in the databases.

Table 1 summarizes the initial operational definitions and data availability per data source, of the eligibility criteria, the exposure and the endpoints. The refined, country-specific definitions of all study variables as well as the final list of other variables with their operational definitions will be provided in the Statistical Analysis Plan (SAP).

Table 1. Preliminary Definitions of the Main Study Variables

Measure	Availability and initial operational definition			
	Denmark France		Sweden	
Ritlecitinib initiation	ATC code L04AF08			
Indicators of Adherence to	RMMs			
Lab: lymphocyte count	Potential candidate example codes (subject to refinement): NPU codes NPU02902 B— Neutrophilocytes; NPU02636 B— Lymphocytes; num.c.	Complete blood count including platelets: TNB code 1104	Not available	
Lab: platelet count	NPU03568 B— Thrombocytes	Complete blood count including platelets: TNB code 1104	Not available	
Screening for TB	Not available	In/outpatient lab test (no results)	Not available	
Screening for viral hepatitis B or C	Not available	In/outpatient lab test (no results)	Not available	
Vaccines	Vaccine type as recorded in the Danish Health Service Registry. The registry lists vaccine pathogen e.g., MMR vaccine etc. However, it is possible to identify live vaccine based on what is used according to the Danish Health Authority. This registry records vaccines that are paid by public. Travel vaccines and vaccines paid by employer will not be recorded.	Reimbursed vaccines such as MMR, chickenpox (for patients 12 months and above), BCG, Rotavirus, varicella, Dengue, and Yellow Fever not reimbursed.	Not available	

Table 1. Preliminary Definitions of the Main Study Variables

Dragnanav	ICD 10 O about an and an fair	ICD-10 codes: O80xx-	ICD-10 O	
Pregnancy	ICD-10 O chapter codes for			
	pregnancy, NOMESCO codes	O84xx (delivery),	chapter codes	
	KMCA for Caesarean and/or	Z37xx (result of	for	
	linkage to the birth registry	delivery), O01xx-	pregnancy	
	Diagnosis codes for	O07xx (abortion and	(https://icd.w	
	pregnancy ICD-10 O chapter	other abnormal	ho.int/browse	
	(https://icd.who.int/browse10/	products of	10/2019/en#/	
	2019/en#/XV)	conception)	XV)	
	(Subject to availability check:		Linkage to	
	referral codes of prenatal	CCAM codes	birth registry	
	visits at GP from the Danish	(medical acts):	may be	
	Health Services Registry)	(delivery)	considered	
	Linkage to birth registry may	JQGD010, JQGD012,		
	be considered	JQGD004, JQGD001,		
		JQGD003, JQGD008,		
		JQGD013, JQGD005,		
		JQGD002, JQGD007,		
		JQGA002, JQGA004,		
		JQGA003, JQGA005		
		(211000,0001000		
		(termination)		
		JNJD001, JNJD002,		
		JNJP001		
		(ectopic pregnancy)		
		JJFA001, JJFC00,		
		JJJA002, JJJC002,		
		JJLJ001, JJPA001,		
		JJPC001, JQGA001		
		331 0001, 3 Q 01 1001		
		Outpatient healthcare		
		code (PRS NAT):		
		(medical termination)		
		2422, 3329, 2415,		
		2416		
Serious infection	Serious infection: ICD-10 code	I.	a hospital	
	contact with a minimum of 1 overnight stay A00-B99, D73.3, E06.0,			
	E32.1, G00-G02, G04.2, G05-G07, H00.0, H44.0, H60.0-H60.3, H66-			
	H67, H70, I30.1, I40.0, J00-J22, J32, J34.0, J36, J38.3, J39.0-J39.1,			
	J44.0, J85, J86, K04.4, K04.6, K04.7, K10.2, K11.3, K12.2, K14.0,			
	K57.0, K57.2, K57.4, K57.8, K61, K63.0, K65, K65.1, K65.2, K65.9,			
	L00-L08, L30.3, M00-M01, M46.2-M46.5, M60.0, M65.0, M71.0,			
	M71.1, M72.6, M86, N10, N11, N12, N13.6, N15.1, N15.9, N30.0			
	N30.8, N34.0, N41.2, N43.1, N45.2, N45.3, N45.4, N48.2, N61, N70,			
	N73, or N75.1, U071			
	Denmark only: Z861A (the code list will be refined in the SAP to map			
	ICD-10-CM codes to ICD-10 equivalents whenever feasible)			

Table 1. Preliminary Definitions of the Main Study Variables

Risk factors for thromboe	mbolic events, malignancy or C	CVD			
Age 65 years or older	per date of birth				
History of thromboembolic events including VTE or ATE	ICD-10 codes I26, I260A I269 I82.2; I82.3, I82.8, I82.9 O22.3 Denmark only: O882D, O882E	3, O87.0, O87.1	, I81, I82.0,		
Malignancy (any, primary or secondary)	ICD-10 codes chapter C	ICD-10 codes chapter C, treatment codes if relevant	ICD-10 codes chapter C		
Major surgery within 90 days of index date	NOMESCO Classification of Operations on the nervous system: KA; Operations on endocrine organs: KB; Operations on the heart and large intrathoracic vessels: KF; Operations on respiratory organs, chest, mediastinum and diaphragm: KG; Breast surgeries: KH; Operations on digestive organs and spleen: KJ; Operations on the urinary tract, male genitalia and retroperitoneal tissue: KK; Operations on female genitalia: KL; Obstetric operations: KM; Operations on the musculoskeletal system: KN	CCAM codes for major surgery	•		
Combined hormonal contraceptives	ATC codes G03A		Not available (not reimbursed)		
Hormone replacement therapy	AT	C codes G03			
Obesity	ICD-10 codes E65				
Alcohol-related conditions	ICD-10 codes K70, F10				
Tobacco-use related conditions	ICD-1	0 codes J40-J47			
Diabetes	ICD-10 codes F	E10-E14, ATC codes A10	1		

Table 1. Preliminary Definitions of the Main Study Variables

Hypertension	ICD-10 codes I10-I15, treatment proxies			
Hyperlipidaemia	ICD-10 codes E78, treatment p	proxies, laboratory data (l	Denmark only)	
Coronary artery disease	ICD-10 codes I21-I25 Nordic Medico-Statistical Committee (NOMESCO) codes for coronary artery bypass graft (CABG) or percutaneous intervention (PCI): FNF, FNG, FNA, FNB, FNC, FND, FNE	ICD-10 codes I21-I25	ICD-10 codes I21-I25 Nordic Medico- Statistical Committee (NOMESCO) codes for coronary artery bypass graft (CABG) or percutaneous intervention (PCI): FNF, FNG, FNA, FNB, FNC, FND, FNE	
Chronic kidney disease	ICD-10 codes N18, potentially dialysis procedure codes	ICD-10 codes N18	ICD-10 codes N18, potentially dialysis procedure codes	
AA diagnosis	ICD	0-10 code L63		

Source of ICD-10 codes: Denmark and Sweden, inpatient (hospital) or outpatient (specialist visits); France, inpatient hospital encounters. ICD-10 codes with trailing letters are applicable in Denmark only.

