8.2. Study Objectives

The study objectives are to:

- 1. Evaluate, to the extent measurable in the available routinely collected data, indicators of HCP's adherence to the risk minimization measures (RMMs) in accordance with the ritlecitinib SmPC, HCP guide, and Patient Card, specifically:
 - Performing laboratory tests of lymphocyte count, platelet count, hepatitis B/C, and tuberculosis (TB) screening prior to initiation of ritlecitinib treatment
 - Performing laboratory tests of lymphocyte count and platelet count at week 4 (± 2 weeks) from initiation of ritlecitinib treatment
 - Avoiding live attenuated vaccines shortly before and during treatment with ritlecitinib
 - No use during pregnancy
 - No use in patients aged < 12 years
 - No use during serious infections
- 2. Describe the characteristics of patients before initiation of ritlecitinib treatment, in terms of:
 - Risk factors for thromboembolic events (including deep vein thrombosis (DVT), pulmonary embolism (PE), and arterial thrombosis)
 - Risk factors for malignancy
 - Risk factors for cardiovascular disease (CVD)

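### The preliminary serious-infection code list in Table 1 misclassifies in both directions: it counts history, sequela and chronic hepatitis codes, and omits N39.0 and I33

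*Protocol*

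**What the plan says.** The objective in Section 8.2 is "No use during serious infections". The matching count in Section 9.7 (item 7) is of patients with a serious infection before the index date.

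The event is defined in the serious-infection row of Table 1 (Section 9.3.7). It requires a listed ICD-10 code at a hospital "contact with a minimum of 1 overnight stay A00-B99, D73.3, E06.0", so the whole of A00-B99 counts. Three further parts of the row matter here:

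- Cardiac: the only I-chapter entries are in the run "H67, H70, I30.1, I40.0, J00-J22, J32, J34.0, J36, J38.3, J39.0-J39.1".
- Urinary: one line ends "M71.1, M72.6, M86, N10, N11, N12, N13.6, N15.1, N15.9, N30.0" and the next continues "N30.8, N34.0, N41.2, N43.1, N45.2, N45.3, N45.4, N48.2, N61, N70".
- Denmark: the row closes with "Denmark only: Z861A (the code list will be refined in the SAP to map", and the sentence goes on to name the purpose of that refinement, which is translation from ICD-10-CM into ICD-10.

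The text before Table 1 calls these definitions initial and leaves the refined definitions of all variables to the SAP. Section 9.7 also lets the SAP modify the protocol's plans.

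**The concern.** An indicator of use during infection needs codes that mark an infection present at the time. A personal-history code records a past one. A sequela code records the after-effects of a past one. A chronic hepatitis code records a standing condition, and the protocol already treats hepatitis B and C through a separate screening indicator. A patient with any of these codes at a qualifying stay would be counted as having had a serious infection.

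Conversely, a patient kept overnight with a urinary infection coded only N39.0, or with endocarditis coded only I33, would be counted as having had none.

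The result is a simple proportion with a 95% CI, reported by country and read as a measure of adherence to a risk minimisation measure. Sampling error shrinks as users accrue; error from the code list does not. Because Z861A applies to Denmark only, it can raise the Danish proportion and no other, which blurs any reading of the three countries side by side.

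**Working it through.** The protocol gives no expected frequency for this indicator, so there is no figure to reproduce. The check is one of membership: each disputed code is compared with the list as printed. Code meanings are the category titles of the WHO ICD-10, which Section 9.3.7 names as the coding system. The protocol does not gloss the codes.

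**Step 1. Codes that are in the list but do not mark a current acute infection**

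| Code | Category | How it enters |
|---|---|---|
| Z861A | under Z86.1, personal history of infectious disease | own entry, Denmark only |
| B90-B94 | sequelae of infectious disease | inside A00-B99 |
| B18 | chronic viral hepatitis | inside A00-B99 |

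**Step 2. Infections that are not in the list**

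| Code | Category | Neighbours that are listed |
|---|---|---|
| N39.0 | urinary tract infection, site not specified | N10, N12, N13.6, N30.0, N30.8, N34.0 |
| I33 | acute and subacute endocarditis | I30.1, I40.0 |

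The line break between N30.0 and N30.8 may have lost a comma or a hyphen. Either way N39.0 is outside: a range from N30.0 to N30.8 ends before it, and the next entries are N34.0 and N41.2. The listed neighbours show that urinary and cardiac infections were meant to be covered, so these look like gaps and not a decision on scope.

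**Step 3. What the list does capture**

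Sepsis (A40, A41) is inside A00-B99. Pneumonia is inside J00-J22, meningitis inside G00-G02, and pyelonephritis is covered by N10 and N12. Peritonitis (K65), osteomyelitis (M86) and COVID-19 (U071) are listed. Some urinary and endocardial cases also enter through a sepsis code, an organism code (B95-B97) or candidal endocarditis (B37.6). The loss in Step 2 is therefore limited to patients with no other listed code.

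**Step 4. Does the announced refinement cure it?**

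Mapping from ICD-10-CM to ICD-10 translates the codes already listed. It has no reason to delete Z861A, B90-B94 or B18, and it cannot add a category that was never listed.

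**Step 5. Effect on the reported proportion**

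Let π be the true proportion with a current serious infection, s the share of those who carry a listed code, and f the share of the others who carry a listed code. The expected reported proportion is

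R = πs + (1 − π)f, so R − π = (1 − π)f − π(1 − s).

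The codes in Step 1 raise f, and the omissions in Step 2 lower s. The two terms have opposite signs, so even the direction of the net error is unknown. Neither term depends on the number of patients. The protocol gives no value for π, s or f, so no size follows.

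**The case against.** The strongest reply is that the list is a draft. The section and the table are both labelled preliminary, final definitions of every variable are promised in the SAP, and Section 9.7 allows the SAP to depart from the protocol. This stands in part: it would be wrong to say that mapping is the only refinement the protocol foresees. But the point concerns codes that the protocol prints, not codes that it leaves open, and the row names a purpose for its refinement that would leave them as they are.

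A second reply is that the overnight stay supplies the severity filter. It does remove most stand-alone minor infection, so listed codes such as common cold (J00), chronic sinusitis (J32) or stye (H00.0) are marginal and are not pressed here. It does not turn a history or sequela code into a current infection, and it cannot recover N39.0 or I33.

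A third reply is that the text just before the overnight-stay condition is broken in the readable copy and may fix the diagnosis position. That is fair. A reader might infer that any stay for another reason qualifies and that a main-diagnosis rule is needed. The documents do not support that firmly. The clause cannot be read, and diagnosis position is described for the French and Swedish sources but not for the Danish one, so such a rule could itself create a difference between countries. The inclusions and omissions above do not depend on that clause.

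Finally, the protocol does not define the Danish extension in Z861A; its meaning here is inferred from the parent category. Section 9.9 concedes that severity is hard to judge for some infections, but it mentions neither history codes nor missing categories.

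**Conclusion.** The point holds as two-way misclassification in a preliminary list. A reader might infer that the indicator does not measure current serious infection at all. The documents do not support that, since the main serious infections are covered (Step 3).

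A reader might also infer that the Danish proportion is materially inflated, or attach a false-positive share to the indicator. Neither can be supported: the protocol gives no frequency for any of these codes, so the size is unknown, and so is the direction of the net error.

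The conclusion rests on two assumptions: that the codes carry their standard ICD-10 meanings, and that Z861A keeps the sense of its parent category. The missing look-back length in Section 9.7, item 7, is a separate matter; settling it would not change which codes count as the event.

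**What to change.** Before extraction, which Section 6 sets for September 2027, edit the serious-infection row of Table 1:

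1. Remove Z861A, B90-B94 (so that A00-B99 is no longer taken whole) and B18.
2. Add N39.0 and I33.
3. Reword the refinement note so that the SAP review covers the clinical content of the list as well as the mapping from ICD-10-CM to ICD-10.

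If the sponsor has a reason to keep or leave out any of these codes, for example a specific meaning of the Danish extension, that reason should be stated in the row. The cost is a small code-list edit. It needs no new data source and no change to the study population or the analysis.

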2. LIST OF ABBREVIATIONS

Abbreviation	Definition
AA	alopecia areata
AE	adverse event
ATC	Anatomical Therapeutic Chemical
ATE	arterial thromboembolism
aRMMs	additional Risk Minimization Measures
AT	alopecia totalis
ATE	arterial thromboembolism
AU	alopecia universalis
BCG	Bacille Calmette-Guérin
CABG	coronary artery bypass graft
CCAM	Classification commune des actes médicaux
CESREES	Comité Ethique et Scientifique pour les Recherches, les Etudes et les
	Evaluations dans le domaine de la Santé
CI(s)	confidence interval(s)
CIOMS	Council for International Organizations of Medical Sciences
CIP	Code Identifiant de Présentation
CNIL	Commission Nationale de l'Informatique et des Libertés
CPR	Central Personal Registry
CVD	cardiovascular disease
DNPR	Danish National Prescription Registry
DVT	deep vein thrombosis
EC	ethics committee
EMA	European Medicines Agency
ENCePP	European Network of Centres for Pharmacoepidemiology and
	Pharmacovigilance
EU	European Union
GPP	Good Pharmacoepidemiology Practices
GVP	Good Pharmacovigilance Practices
HCP	healthcare professional
HMA	Heads of Medicines Agencies
ICD	International Statistical Classification of Diseases
ICD-10	International Classification of Disease, Tenth Revision
ICD-11	International Classification of Disease, Eleventh Revision
IRB(s)	Institutional Review Board(s)
ISPE	International Society for Pharmacoepidemiology
JAK	Janus Kinase
KVÅ	Klassifikation av vårdåtgärder
MAH	Marketing Authorization Holder
MMR	measles, mumps, rubella
NI	non-interventional
NIS	non-interventional study

PFIZER CONFIDENTIAL

Abbreviation	Definition
NMSC	nonmelanoma skin cancer
NOMESCO	Nordic Medico-Statistical Committee
NPU	Nomenclature, Properties and Units
PAS	Post-authorization studies
PASS	Post-authorization safety study
PCI	Percutaneous intervention
PE	pulmonary embolism
PY(s)	person-year(s)
RMMs	Risk Minimization Measures
RWD	real world data
SAP	Statistical Analysis Plan
SmPC	Summary of Product Characteristics
SNDS	Système National des Données de Santé
TB	tuberculosis
UCD	Unité Commune de Dispensation
US	United States
VTE	venous thromboembolism
WHO	World Health Organization

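### Section 9.3.4 counts NMSC separately from malignancy, but Table 1 defines malignancy to include it, so a single NMSC diagnosis scores two malignancy risk factors

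*Protocol*

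**What the plan says.** Section 9.3.4 gives six risk factors for malignancy, looked for in the 12 months up to and including the index date: age over 65, "History of malignancy", "History of NMSC", obesity, alcohol-related conditions and tobacco-related conditions. The abbreviation list expands NMSC as "nonmelanoma skin cancer".

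Table 1 (section 9.3.7) has one block of definitions for the thromboembolic, malignancy and CVD risk factors. Its only malignancy row is labelled "Malignancy (any, primary or secondary") and is defined by "ICD-10 codes chapter C" in all three countries, with treatment codes added in France if relevant. The row excludes no cancers. The table has no NMSC row.

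Section 9.7, item 9, asks for the patients with measured risk factors and the "number of risk factors for malignancy within 12 months before index date". It states no hierarchy or de-duplication rule. Section 9.3.7 calls the definitions initial and leaves the refined versions to the SAP.

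**The concern.** A count of risk factors is interpretable only if each unit stands for a distinct feature of the patient. Here two of the six items are nested: under the Table 1 definition, everyone with a recorded NMSC also has a recorded malignancy. One skin cancer diagnosis therefore adds two to the count, and one cancer of any other kind adds one.

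Describing malignancy risk factors before initiation is part of Objective 2, one of the study's two objectives. The nesting raises the reported share with a history of malignancy, the mean number of malignancy factors and the share of patients with two or more.

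There is also a practical reason to settle it early. Under section 9.6, investigators in each country build their own analytic dataset and send aggregate output to the coordinating institution. If one team nests NMSC within malignancy and another separates it, the country tables will not be comparable, and the difference cannot be repaired from aggregates.

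**Working it through.** The protocol gives no figure for the malignancy count or for NMSC prevalence, so there is nothing to reproduce on this point. The check is a tally of the definitions, followed by the arithmetic that results.

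**Inputs.** The six-item list is from 9.3.4. The chapter C definition is from Table 1. The count is from 9.7, item 9. The reference size of 385 patients per database is from 9.5. It reproduces as 0.5 × 0.5 × 1.96² / 0.05² = 384.2, rounded up to 385.

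**Tally.** Let N be a recorded NMSC and O any other recorded cancer in the lookback. Table 1 sets history of malignancy if N or O is present. The contribution of the two cancer items to the count is:

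| Cancer records in lookback | As written | Mutually exclusive items |
|---|---|---|
| None | 0 | 0 |
| Other cancer only | 1 | 1 |
| NMSC only | 2 | 1 |
| NMSC and another cancer | 2 | 2 |

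Only the NMSC-only row changes. A patient with NMSC and a second cancer scores two either way, and correctly so.

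**Size.** Let q = P(N and not O), the share of patients with NMSC only. Then:

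- Mean malignancy count: as written minus exclusive = (2 − 1) × q = q.
- Share with a history of malignancy: P(N or O) − P(O) = q.
- Share with two or more malignancy factors: this changes only for NMSC-only patients who have none of the other four factors, so it is too high by at most q.

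The protocol does not give q. Under assumed values:

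| Assumed q | Patients affected, 385 × q | Excess in mean count |
|---|---|---|
| 0.5% | 1.925 (about 2) | 0.005 |
| 1% | 3.85 (about 4) | 0.01 |
| 2% | 7.7 (about 8) | 0.02 |

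**The case against.** The strongest reply is that Table 1 is expressly preliminary and that refined definitions of all study variables are promised in the SAP, so a missing NMSC row is only a code list not yet written. It is true that the SAP can cure this. But the protocol does more than leave a gap: it states a definition, any malignancy in chapter C, which produces a double score when set beside 9.3.4 and item 9. The Danish lymphocyte codes and the serious-infection list are individually marked for refinement; the malignancy row is not. A SAP that copies the row faithfully will carry the error forward.

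A second reply is that the row's label does not match the wording in 9.3.4, so it may not be meant for that list. It is, however, the only malignancy definition in the table, and its block is headed as serving all three lists.

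A third reply is that NMSC may be listed as a subset for separate display. Section 9.3.3 also lists items that can overlap, such as arterial thromboembolism and CVD. This stands as far as intent goes: the separate listing does not prove that the authors meant malignancy other than NMSC. It does not rescue the count, because a subset shown for display should still be counted once.

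A reader might also infer that the thromboembolic count is inflated, since an NMSC patient scores the malignancy item there too. The documents do not support that. Section 9.3.3 lists malignancy without a separate NMSC item, Table 1 says any malignancy, and the two agree. Nothing is counted twice, and nowhere does the protocol say NMSC should not count on that list.

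**Conclusion.** The point holds for the malignancy list. As written, one NMSC diagnosis sets two of the six factors in 9.3.4, and the mean count is too high by exactly the share of patients with NMSC only. At an assumed share of 0.5% to 2%, that is about 2 to 8 of 385 patients. At the low end, the masking of counts from 1 to 4 in section 9.10 could hide the NMSC cell itself.

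Two limits apply. First, the protocol gives no NMSC code, so the overlap rests on NMSC being a cancer and on the row covering any malignancy. Second, it would be too broad to say that every patient with NMSC is over-counted. The error needs a code within the 12-month lookback, from inpatient or specialist outpatient contacts in Denmark and Sweden or inpatient encounters in France, and no other cancer code.

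A reader might also infer a several-fold error in the share with multiple risk factors. That would depend entirely on assumed prevalences and on leaving some of the six factors out. What can be said without such assumptions is that the excess in that share is at most the NMSC-only share. The adherence indicators, the study size and the thromboembolic and CVD counts are not affected. This is a small, well-defined error in a descriptive output and is worth correcting before programming starts.

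**What to change.** For the 9.3.4 list and the item 9 count, define history of malignancy as ICD-10 chapter C excluding the NMSC codes, and add a separate NMSC row with its own codes to Table 1, so that one code cannot set both factors. Carry the same two definitions into the SAP for all three countries.

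Leave the any-malignancy definition in place for the thromboembolic list in 9.3.3. The history-of-malignancy share under 9.3.4 will then differ from the any-malignancy share under 9.3.3, and the tables should label the two accordingly.

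The cost is one edited and one added code row, plus the labels. No new data are needed.
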